### 9.3. The Level of Statistical Significance

A 5% significance level will be used for testing effects in the whole cohort and a 1% significance level for the testing of subgroup interactions, as per the sample size calculation.

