## 1.9. Sample size

938 children are required (for alpha=0.01, 90% power, 80% follow-up) to detect a 3 day difference in the effect of antibiotics for the primary outcome among any one of 5 clinical subgroups (see below). We assume a subgroup represents at least 30% of the sample (our data suggests 30-65% for each of the key subgroups).

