## 5.15. Sample size calculation

Pilot phase: there is no sample size calculation.

Main phase: An alpha of 0.01 is chosen to allow for 5 pre-specified subgroups, which occur in at least 30% of children based on our previous data (sputum (65%), fever (64%); generally unwell rated as a bad problem (30%); short of breath (36%) abnormal chest signs (crepitations: 43% ). Previous consensus documented less than 2-3 days difference in symptoms rated moderately bad or worse is unlikely to be a sufficient reason to prescribe antibiotics, and 3 days should probably now be the minimum given the short and long term disadvantages of antibiotics, (9, 10) and in particular increased national and international concern over the danger of antibiotic resistance (<https://www.gov.uk/government/publications/resources-to-support-the-2012-european-antibiotic-awareness-day-in-england>; <https://www.gov.uk/government/news/prime-minister-warns-of-global-threat-of-antibiotic-resistance> ). (3, 4) To detect a hazard ratio for the treatment interaction of 1.7 (see Appendix 2 to this protocol: equivalent to 3 days difference between a subgroup and the whole sample), for the smallest subgroup of interest (30% of the sample), using the equations of Schmoor et al requires 738 individuals for 80% power and 938 individuals for 90% power (assuming 80% follow-up). (36) The other (larger subgroups) will have greater power. To allow for some leeway in our assumptions we will aim to recruit at least 1000 children.

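### Optional improvement: the fixed 1% level for each of the five subgroup interactions is valid, but Holm's procedure would find somewhat more at the same 5% family-wise error when several interactions are real

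*Protocol*

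**What the plan says.** Protocol section 9.3 gives two levels. For the overall comparison, "A 5% significance level will be used for testing effects in the whole cohort". For effect modification it sets "a 1% significance level for the testing of subgroup interactions, as per the sample size calculation".

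The reason is in section 5.15: "An alpha of 0.01 is chosen to allow for 5 pre-specified subgroups". Bonferroni is not named, but five tests at 1% add up to 5%, so the rule is single-step Bonferroni in substance. No step-down or other sequential rule appears.

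The design target is one interaction at a time. Section 1.9 describes detecting a difference "for the primary outcome among any one of 5 clinical subgroups". Section 5.15 sizes the trial "To detect a hazard ratio for the treatment interaction of 1.7", "for the smallest subgroup of interest (30% of the sample".

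Two further statements bear on the wording of any change. Section 1.10 calls the list of five subgroups provisional, to be finalised blind in the analysis plan. Section 9.1 plans an interaction term for each subgroup on every outcome, not only the primary one.

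**The concern.** The trial's stated purpose is to learn which groups of children benefit. Sections 3 and 3.1 argue that an average effect alone would not persuade prescribers, and the lay summary speaks of groups in the plural. The five features also overlap. The prevalences in section 5.15 (65%, 64%, 30%, 36% and 43%) sum to 238%, or about 2.4 features per child if they describe one population. If amoxicillin helped sicker children, more than one interaction could be real.

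That is the situation in which a fixed 1% gives up power. Once one interaction has been established, at most four null hypotheses can still be true, so 5%/4 would protect the remainder, but the protocol keeps testing at 5%/5. The possible loss is a real interaction left undeclared although the 5% error budget had room for it.

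**Working it through.** **Inputs.** From the protocol: five interactions, 1% each (5.15, 9.3), and 90% power per interaction (1.9, 5.15). Assumed: two-sided tests, since sidedness is not stated. The ratio of the two stated sample sizes, 938/738 = 1.271, fits two-sided 1% (1.274) better than one-sided 1% (1.297). Also assumed: correlation between test statistics of 0 or 0.3, and equal power for every real interaction.

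**Step 1: reproduce the 1%.** 0.05/5 = 0.01. With independent tests and no real interaction, the chance of at least one false claim is 1 - 0.99^5 = 4.9%. The level reproduces as Bonferroni for five tests.

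**Step 2: Holm thresholds.** Ordered from the smallest p-value: 0.05/5 = 1%, 0.05/4 = 1.25%, 0.05/3 = 1.67%, 0.05/2 = 2.5%, 0.05/1 = 5%, stopping at the first failure. The first step equals the level in the sample size calculation, so the required number of children does not change.

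**Step 3: power of one test at each threshold.** 90% power at two-sided 1% means an expected z of 2.576 + 1.282 = 3.857 (from unrounded values). Power at level a is Φ(3.857 - z(1 - a/2)), giving 90.0%, 91.3%, 92.8%, 94.7% and 97.1% at the five thresholds.

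**Step 4: the two rules compared.** Simulation of 400,000 sets of five two-sided z-tests, independent, with 90% power for each real interaction (fixed 1% → Holm):

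| Real interactions | Mean gain per real interaction (points) | All real ones detected | At least one false claim |
|---|---|---|---|
| 1 | about 0.1 | 90.0% → 90.1% | 4.0% → 4.8% |
| 2 | 1.3 | 81.0% → 83.5% | 3.0% → 4.6% |
| 3 | 2.6 | 73.0% → 80.2% | 2.0% → 4.6% |
| 4 | 4.3 | 65.7% → 80.4% | 1.0% → 4.5% |
| 5 | 6.6 | 59.1% → 85.9% | not applicable |

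The fixed-1% entries for all real ones detected can be checked by hand: 0.9^2 = 81.0%, 0.9^3 = 72.9%, 0.9^4 = 65.6%, 0.9^5 = 59.0%.

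Over correlations 0 to 0.3, the chance of detecting every real interaction goes from 81-82% to 84% (two real), 73-76% to 80-82% (three) and 59-66% to 86-87% (five). At correlation 0.3 the false-claim figures for two, three and four real are 2.9% → 4.5%, 2.0% → 4.3% and 1.0% → 4.3%. In no setting did Holm lose a Bonferroni rejection or exceed 5% family error beyond simulation error. The chance of finding at least one real interaction agreed to within about 0.1 point.

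**Step 5: sensitivity to the assumed power.** A standard interaction formula, events = (2.576 + 1.282)² / [0.25 × 0.3 × 0.7 × (ln 1.7)²], gives 1007 events, or about 1258 children at 80% follow-up. That does not reproduce the stated 938. On this formula 938 children give 77.5% power. The source of the cited method is not available here and 1:1 allocation is assumed, so this is a separate question and the comparison does not depend on it. At 77.5% power the mean gains are 1.9, 4.0, 6.9 and 11.0 points for two to five real interactions.

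**The case against.** The strongest reply is that nothing here is wrong. A fixed 1% is valid, pre-specified and consistent across sections 1.9, 5.15, 9.3 and Appendix B. It also meets the stated design target: for any one subgroup, Holm changes power from 90.0% to about 90.1%. All of that stands.

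The second reply is that the gain is not free. It arises only when several interactions are real, and in those same settings Holm uses more of the error budget. With three real interactions, average power rises by 2.6 points while the chance of a false subgroup claim more than doubles. The error for each null subgroup goes from 1.0% to 2.4% with independent tests. A false claim would suggest benefit where there is none, in a trial whose section 5.15 sets a demanding threshold because of antibiotic resistance. A team could reasonably prefer to keep 1% per subgroup. This stands as a trade-off, but the risk stays within the 5% that the choice of 1% for five tests already accepts.

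The third reply is that the number of real interactions is unknown. Section 5.15 gives prevalences only, and section 3 reports modest benefit in adults even in important subgroups. This stands too: several real interactions is a plausible scenario, not something the protocol asserts.

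That the analysis plan is not shown does not dispose of the point, because section 9.3 itself fixes the level.

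**Conclusion.** This is a cheap, optional improvement and not a correction. Fixed 1% controls the family-wise error but is less powerful than Holm at the same 5%. At 90% power per interaction, the average gain is about 1 point with two real interactions, 2 to 3 with three, 4 with four and 6 to 7 with five. It is essentially nil with one.

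A reader might infer that the 1% rule leaves the trial underpowered or is a mistake. The documents do not support that: the rule is valid, the sample size is built on it, and the stated target of any one subgroup is unaffected. A reader might also take the rise from 59-66% to 86-87% as the expected benefit. That figure needs all five interactions to be real, each at the design effect, which the protocol nowhere assumes. With two or three real, the chance of detecting all of them rises by roughly 2 to 7 points.

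The sizes rest on two-sided tests, equal power per real interaction and correlations of 0 to 0.3. Holm's error control and its never losing a Bonferroni rejection need none of these assumptions.

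**What to change.** If the team accepts the trade-off, reword the interaction clause of section 9.3 along these lines, before unblinding:

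*The m pre-specified clinical subgroup interactions on the primary outcome (m = 5 unless the final list, agreed blind to allocation, differs) will be tested with Holm's procedure at a family-wise 5% level; for m = 5 the thresholds are 1%, 1.25%, 1.67%, 2.5% and 5% in order of p-value. A 99% confidence interval will be reported for each interaction. Interactions on other outcomes will be tested at 1%.*

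Writing m instead of five respects the provisional list in section 1.10. A fixed 1% would allow 4% in total with four subgroups and 6% with six. The last sentence keeps a stated level for the other interactions planned in section 9.1.

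The cost is a short paragraph, with no extra children or data and no change to the sample size. There are two downsides to accept openly. A 99% interval may include 1 for an interaction that Holm declares significant at a later step. The chance of a false subgroup claim also rises when real and null interactions are mixed, though it stays within 5%. If the team prefers the simpler rule, section 9.3 can stand as it is.

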### 9.4. Procedure for Accounting for Missing, Unused, and Spurious Data

The primary analysis will be a complete case analysis and a secondary analysis will be carried out using imputation (by documenting the change in estimates for a range of assumptions about resolution of symptoms among those with missing data, and using multiple imputation as appropriate).

### 9.5. Inclusion in Analysis

The primary analysis will be a complete case analysis on an intention to treat basis (i.e. whether or not children complied with antibiotics. A per protocol analysis among children where more than 5 days (approximately 80%) of the medication was used will be performed.

## 10. DATA MANAGEMENT

### 10.1. Source Data

Source documents are where data are first recorded, and from which participants' CRF data are obtained. Source documents will be comprised of the following:

- Case report forms (CRF) for baseline assessment, follow-up and study discontinuation (completed by researchers in consultation with participant or their healthcare professional)
- Medical records (from which medical history and previous and concurrent medication may be summarised into the CRF or entered directly into Research Online)
- Laboratory results
- Diaries (hard copies completed by parents/guardians/participants)
- Correspondence (provided by participants, their healthcare professional or researcher).

All documents will be stored safely in confidential conditions. On all study-specific documents, other than the signed consent, assent and baseline contact information page, the participant will be referred to by the study participant number/code, not by name.

## 10.2. Access to Data

Direct access will be granted to authorised representatives from the Sponsor, host institution and the regulatory authorities to permit study-related monitoring, audits and inspections.

Raw study data will be protected as far as is possible by the release being made following all investigations described in this Protocol and the associated study Publication Policy and Data Management Plan. We shall make data available to the scientific community once the analysis described in the protocol is complete. Interested parties may contact the corresponding author ([name], [contact]) in order to discuss the data and when it will be available for release.

## 10.3. Data Recording and Record Keeping

Study data will be entered, or transferred, into Research Online (RO). Participants will only be identified by a study-specific participant number and/or code in the Research Online database. Documents containing participant identifiable information will be stored separately from other study documents and saved within a securely hosted database separate from Research Online.

Research Online is a software package designed to capture, manage and store clinical study data. Its usage enables compliance with Good Clinical Practice (GCP) and regulatory guidelines by offering differentiated user roles and privileges, password and user authentication security, electronic signatures, SSL encryption, de-identification of protected health information and comprehensive auditing to record and monitor access and data changes.

Research Online databases and web servers are hosted in data centers that meet the highest available standards for security. The servers are actively monitored to prevent failure (including memory, storage, CPU usage and network connections). Backups of all data are made on a daily basis. Backups are stored in secured locations that are geographically dispersed. Back-ups will be stored one year.

All Data Management functions will be performed in accordance with CTU DM SOPs. A Data Management Plan (DMP) is in place for all CTU hosted trials, outlining in detail the study specific procedures to ensure that high quality data is produced for statistical analysis. The DMP is reviewed and signed by all applicable parties, including the Study Manager and the Trial Statistician, prior to the first patient being enrolled.

Clinical study data will be collected by the CTU in paper format, direct data capture, and also direct upload of study data from external data sources (laboratory test results). The final repository for all study data will be Research Online. All Study Data Documents (SDDs) in paper format are date

stamped upon receipt and tracked within a study management database. A full pre-entry review ensures that all pages have been received, subject identifiers are consistent and obvious errors/missing data are appropriately addressed prior to entry. All paper SDDs are entered by independent data entry staff into the clinical database.

Data validation for all data entered into the clinical database is achieved by programming study specific checks at point of entry, or by execution of SQL based queries. The Clinical Data Manager will review all discrepancies and generated output. If clarification from a research site is required, the query is added to a Data Verification Site (DVS) Report, and subsequently issued. The Clinical Data Manager oversees the tracking of DVS reports until they are resolved, and applies any updates to the clinical database.

Prior to database lock, dataset review is performed by the Clinical Data Manager and the Trial Statistician. All critical data items are 100% checked against original SDDs (and subsequent updates) to ensure accuracy, and an error rate is established across all fields to ensure a consistently accurate dataset.

At the conclusion of the study and after the database has been locked, all essential documents will be archived until 3 years after the youngest participant reaches 18 years old. The Chief Investigator is responsible for authorising retrieval and disposal of archived material.

## 11. QUALITY ASSURANCE PROCEDURES

The study will be conducted in accordance with the current approved protocol, ICH GCP, relevant regulations and standard operating procedures. Regular monitoring will be performed according to ICH GCP. Data will be evaluated for compliance with the protocol and accuracy in relation to source documents. Following written standard operating procedures, the monitors will verify that the clinical study is conducted and data are generated, documented and reported in compliance with the protocol, GCP and the applicable regulatory requirements.

Healthcare professionals participating in our study will be asked to submit proof that they have completed GCP training, or be required to undertake GCP training (e.g. register for the online GCP course provided by the CRN team or attend local face to face training).

The Study Management Group (SMG) will be responsible for the monitoring of all aspects of the trial's conduct and progress and will ensure that the protocol is adhered to and that appropriate action is taken to safeguard participants and the quality of the trial itself. The SMG will be comprised of individuals responsible for the study's day to day management (e.g. the CI, study manager, statistician, data manager) and will meet regularly.

The Study Steering Committee (SSC) will be convened to provide overall supervision of the trial and ensure that it is being conducted in accordance with the principles of GCP and the relevant regulations. The SSC will consist of at least 5 members including the Chief Investigator, a co-investigator and an independent member.

An independent Data and Safety Monitoring Committee (DSMC) will review the accruing study data after each winter during the study recruitment period and assess whether there are any safety issues that should be brought to participants' attention or any reasons for the study not to continue. The DSMC will consist of an independent statistician and at least 2 independent members.

## 12. SERIOUS BREACHES

The Medicines for Human Use (Clinical Trials) Regulations contain a requirement for the notification of "serious breaches" to the MHRA within 7 days of the Sponsor becoming aware of the breach.

A serious breach is defined as "A breach of GCP or the study/trial protocol which is likely to affect to a significant degree:

- (a) the safety or physical or mental integrity of the subjects of the study; or
- (b) the scientific value of the study.

In the event that a serious breach is suspected, the Sponsor must be contacted within 1 working day. In collaboration with the CI, the serious breach will be reviewed and, if appropriate, the Sponsor will report it to the REC, Regulatory Authority and the NHS host organisation within 7 calendar days.

## 13. ETHICAL AND REGULATORY CONSIDERATIONS

### 13.1. Declaration of Helsinki

The Investigator will ensure that this study is conducted in accordance with the principles of the Declaration of Helsinki.

### 13.2. ICH Guidelines for Good Clinical Practice

The Investigator will ensure that this study is conducted in full conformity with relevant regulations and with the ICH Guidelines for Good Clinical Practice (CPMP/ICH/135/95) July 1996.

### 13.3. Approvals

The protocol, informed consent form, participant information sheet and any proposed advertising material will be submitted to an appropriate Research Ethics Committee (REC), regulatory authorities (MHRA in the UK), and host institution(s) for written approval.

The Investigator will submit and, where necessary, obtain approval from the above parties for all substantial amendments to the original approved documents.

### 13.4. Reporting

The CI shall submit once a year throughout the clinical study, or on request, an Annual Progress Report to the REC, host organisation and Sponsor. In addition, an End of Study notification and final report will be submitted to the MHRA, the REC, host organisation and Sponsor.

### 13.5. Participant Confidentiality

The study staff will ensure that the participants' confidentiality is maintained. Other than on the contact information sheet, consent form and, if applicable, assent form, participants will be identified only by a participant ID number on the CRF and any electronic database. All documents will be stored securely and only accessible by study staff and authorised personnel. The study will comply with the Data Protection Act which requires data to be anonymised as soon as it is practical to do so.

### 13.6. The blood and throat swab samples provided in ARTIC PC

The University of Southampton as the lead centre, and as being responsible for contracting, as the 'Suppliers' of the blood and throat swabs confirms that any 'Material' subject to The Human Tissue Act 2004 consent provisions has been obtained with full, informed consent of the donor for its use as detailed in the protocol for the Study, and as outlined in the current, approved version of the patient information sheet and consent form. If applicable, these documents will be provided in conjunction with this agreement. The laboratories, or Biobank, the 'Recipients', shall keep the Material secure at the Recipient's laboratory and ensure that access to the Material is restricted to the Recipient and authorised co-workers as detailed in the current ethically approved research ethics application form and protocol for the Study. In this agreement 'the Material' shall include any and all materials, documents and information that the Supplier may provide to the Recipient. All documents and information provided with the Materials, including patient data shall be considered confidential. The Recipient agrees not to transfer or distribute any part of the Material or any extracts, replications, summaries or derivatives thereof to any third part with the prior approval of the Supplier, Study sponsor and any relevant ethics committee. The Recipient will confirm that the disposal, where applicable, of any remaining Material will be carried out in line with local disposal policies relating to the disposal of human tissue and in accordance with The Human Tissue Act 2004.

## 14. FINANCE AND INSURANCE

## 14.1. Funding

The study is funded by a National Institute for Health Research Health Technology Assessment Programme: REF: 13/34/64.

## 14.2. Insurance

The University of Southampton has a specialist insurance policy in place which would operate in the event of any participant suffering harm as a result of their involvement in the research. NHS indemnity operates in respect of the clinical treatment which is provided.

## 15. PUBLICATION POLICY

The investigators will be involved in reviewing drafts of the manuscripts, abstracts, press releases and any other publications arising from the study. Authors will acknowledge that the study was funded by a National Institute for Health Research Health Technology Assessment Programme Ref: 13/34/64. The publication policy for this Grant will state the lead author(s) and co-authors for each manuscript. Authorship will be determined in accordance with the ICMJE guidelines and other contributors will be acknowledged.

## 17. Appendix A: Protocol Change Control

Version	Date	Summary of Changes	Author
V1.0	30 September 2015		[name]
V2.0	22 January 2016	Removal of Co-amoxyclav as antibiotic in pilot phase, amended timetable, amended QoL measures, addition of thank you to parent/child, clarity of in and exclusion criteria.	[name]
V3.0	04 March 2016	Clarity re samples and the Human Tissue Act 2004.	[name]
V4.0	22 April 2016	Inclusion of analysis of viral samples. Inclusion of potential to store, subject to consent, samples for future research.	[name]
V4.1	10 May 2016	Correction of spelling in section 1.7	[name]
V5.0	29 July 2016	Clarity over exclusion criteria and sub group analysis, and amending Health Economic tools	[name]
V6.0	17 February 2017	Removing [name] adding [name] [name] as a Protocol contributor. Adding an exclusion criteria of 'Suspected Bordetella pertussis' amending wording to allow recruitment in Children's Emergency Departments, clarity over statistical methods, adding in new PPI members and their roles.	[name]
V6.1	06 March 2017	Removing 'Confidential' from the front of the Protocol	[name]
V7.0	14 June 2017	The Protocol now includes the statement 'At the end of the analysis described in this Protocol we will share anonymised data with other researchers after consideration of a request in writing to the Chief Investigator. We shall make	[name]

		
data available to the scientific community with as few restrictions as feasible, while retaining exclusive use until the publication of major outputs' in the section 10 Data management sub section 10.2 Access to data. The reference to the NICE sepsis guideline has been updated as this is now published, [name] has been removed as a collaborator and [name] added as Steering committee statistician.
	
V8.0	24 July 2017	Removal of confidential statement from front page. Clarity given about IMP storage given new stability data.	[name]
V9.0	10 August 2017	Section 6.2 is amended to fit with stability data as accepted by the Sponsor	[name]

